DETERMINATION OF SERUM FENTANYL LEVELS AFTER USING REFERENCE AND GENERIC TRANSDERMAL FENTANYL PATCHES WITH AND WITHOUT STANDARDIZED HEAT APPLICATION IN HEALTHY HUMAN VOLUNTEERS

Short title: The Effect of Heat on Fentanyl Release from Fentanyl Patches in Healthy Adults

Clinical Protocol Principal Investigator:

[name], MS

U01 Principal Investigator(s):

[name] (contact), PhD

[name]

Sponsor:

Food and Drug Administration

Grant Number: 1U01FD004955-01

Version 8.0

12 June 2017

STATEMENT OF COMPLIANCE

This study will be conducted in compliance with the protocol, International Conference on Harmonisation Good Clinical Practice E6 (ICH-GCP) and the applicable Food and Drug Administration and other Department of Health and Human Services regulatory requirements.

All key personnel (all individuals responsible for the design and conduct of this study) have completed Human Subjects Protection Training.

PROTOCOL SUMMARY

Title:	Determination of Serum Fentanyl Levels after using Reference and Generic Transdermal Fentanyl Patches with and without Standardized Heat Application in Healthy Human Volunteers	
Population:	Healthy adults age 18 – 45 years	
Number of Sites:	Single site: University of Maryland School of Medicine	
Study Duration:	Approximately 18 weeks including the screening period	
Subject Participation Duration:	Approximately 12 weeks including the screening period	
Description of Study Product:	Fentanyl (Duragesic [®] , matrix type, Janssen Pharmaceutics; Mylan (fentanyl) matrix type, Mylan Pharmaceuticals and Apotex (fentanyl) matrix type, Apotex Corp.) transdermal patches, and naltrexone hydrochloride tablet and naloxone hydrochloride injections	
Objective:	To determine serum fentanyl levels after using reference (Duragesic [®]) and generic fentanyl (Mylan and Apotex) transdermal patches with and without standardized heat application in healthy adult volunteers	
Description of Study Design:	The study will be an open-label, study with six procedure days (n=10 healthy subjects completing all 6 procedure days) with at least two weeks between each procedure day and the subsequent one.	
	Each of the 10 subjects will be enrolled to complete all six procedure days. For each of the fentanyl products ($n=3$) there will be two procedure days, and on all procedure days the patches will be applied for 19 hours.	
	The study will contain six procedure days:	
	• Procedure Day 1: The heating pad will be set to induce a skin temperature of 42.0 \pm 2°C and applied for 1 hour, 11 hours after application of the Apotex (fentanyl) transdermal patch (25 µg/h).	
	• Procedure Day 2: The heating pad will be set to induce a	

skin temperature of 42.0 \pm 2°C and applied for 1 hour, 18 hours after application of the Apotex (fentanyl) transdermal patch (25 µg/h).

- Procedure Day 3: The heating pad will be set to induce a skin temperature of 42.0 ± 2°C and applied for 1 hour, 11 hours after application of the Duragesic[®] transdermal patch (25 µg/h).
- Procedure Day 4: The heating pad will be set to induce a skin temperature of 42.0 ± 2°C and applied for 1 hour, 18 hours after application of the Duragesic[®] transdermal patch (25 µg/h).
- Procedure Day 5: The heating pad will be set to induce a skin temperature of 42.0 ± 2°C and applied for 1 hour, 11 hours after application of the Mylan (fentanyl) transdermal patch (25 μg/h).
- Procedure Day 6: The heating pad will be set to induce a skin temperature of 42.0 ± 2°C and applied for 1 hour, 18 hours after application of the Mylan (fentanyl) transdermal patch (25 μg/h).

2 BACKGROUND INFORMATION AND SCIENTIFIC RATIONALE

2.1 Background Information

There are numerous transdermal drug delivery systems (TDDS) that are currently available in the United States, the first of which was approved by the Food and Drug Administration (FDA) in 1979 [1]. TDDS are very attractive, convenient and easy to use systems and are available in various forms including patches (matrix or reservoir), sprays, gels, and ointments. Drug release from these TDDS varies significantly and is dependent on a number of factors including system design, physicochemical properties of the drug, excipients, occlusion, sweat, skin condition, skin type and temperature. Investigating the influence of these factors on drug release from reference and generic products that are often available in different forms is important to ensure that generic products are not less safe than the reference product. In this proposal we will focus on investigating the influence of heat on drug release from reference and generic products that are available in matrix systems. Systemic absorption of drugs is dependent on cutaneous blood flow. Application of, or exposure to heat, allows gradual increase in cutaneous blood flow and an increase in the absorption rate. Indeed, exposure to heat has been demonstrated to increase drug release from TDDS, which led to increased serum concentrations of numerous drugs (e.g., fentanyl and nicotine) and raised a number of safety concerns [2-8]. As a result, almost all TDDS that are currently available have warnings against heat exposure. The issue is, if a reference product has a warning against applying heat, the generic product will have the same warning regardless of the dissimilarity that may exist between them (i.e., differences in inactive ingredients or type of TDDS), and it is possible that release rate and absorption rate of the same drug differs from different TDDS in response to heat.

2.2 Rationale

The objective of this proposal is to conduct in vivo studies to compare the influence of heat on fentanyl drug release from FDA approved TDDS products (reference e.g. Duragesic[®], versus generic products e.g. Apotex and Mylan transdermal patches) that have different inactive ingredients. While there is data in the literature for heat effect on different active pharmaceutical ingredients (API's), specifically reference listed drugs (RLD), from exposure to heating blankets, sauna, hot showers, exercising, there is no head to head comparisons for heat effect on RLD versus generic drugs. This study will help support policy development for characterization of heat effects for future generic applications. Furthermore, if in-vitro in-vivo correlation (IVIVC) can be established, then in vitro studies can be used for generic applications in the future, which would mitigate

exposure of human beings to out of label studies. This approach will help ensure that patients would not be subjected to additional risks if they use a generic TDDS rather than its respective reference product.

Fentanyl was selected for this study because it is a drug with significant and well characterized heat effect studies in the literature, and for which an antidote exists. Fentanyl has the most variability available in terms of generic transdermal systems with different formulations that are approved and already on the market. This study will provide data that could potentially help us determine if one formulation/adhesive is more prone to heat effect/changes in delivery compared to another. Furthermore by demonstrating IVIVC then in vitro studies can be conducted on generic fentanyl transdermal patches in the future without the need to subject human volunteers to additional testing. To mitigate the potential risk of a higher absorption of fentanyl through the skin, the lowest strength patch is being used in this study (25 µg/hr).

Duragesic® versus Apotex (fentanyl) and Mylan (fentanyl) transdermal patches

	Duragesic [®]	Apotex (fentanyl) patch	Mylan (fentanyl) patch
Inactive ingredients	Alcohol, ethylene vinyl acetate-copolymer	Isopropyl myristate, octyldodecanol, polybutene	Dimethicone NF, polyolefin film backing,
	membrane and hydroxyethyl cellulose, polyester film backing, silicone adhesive	and polyisobutene adhesive	silicon adhesive
TDDS type	Matrix	Matrix	Matrix
Manufacturer	Janssen	Apotex	Mylan

3 OBJECTIVES

3.1 Study Objectives

Rate of drug release and kinetics of drug absorption could vary from patches with different dosage form designs. The influence of heat on reference vs. generic products that are formulated differently impose a critical safety issue for users of generic TDDS. As such, the main objective of this project is to determine serum fentanyl levels after using reference (Duragesic[®], matrix type patch, Janssen Pharmaceutics) and generic fentanyl (Apotex and Mylan) transdermal patches with and without standardized heat application in healthy adult volunteers.

3.2 Study Outcome Measures

The main outcome measure of the study is the measurement of maximum serum concentration (Cmax); time of maximum serum concentration (Tmax) of fentanyl and area under the curve (AUC) attained with and without heating in each of the three fentanyl patches (reference and generic).

4 STUDY DESIGN

This is an open-label, non-placebo controlled pharmacokinetic (PK) assessment study. The study will consist of six-procedure days (10 subjects) with at least two weeks between procedure days. The half-life of fentanyl is approximately 24 hours. Hence, 7 days (i.e. 5 half-lives) will be sufficient for >95% of fentanyl to be eliminated from the body. Each of the 10 subjects will be enrolled to complete all six procedure days (Procedure Days 1 to 6). The study is open label and not blinded, because PK assessment is not subject to participant and/or observer bias. After each procedure session (procedure day) is completed, the available safety data will be reviewed by an Independent Safety Monitor (ISM) to determine whether or not to proceed to the next procedure day.

The six procedures days are as follows:

Procedure Day 1: An **Apotex** (fentanyl) patch will be applied without heat for 11 hours, then a theratherm® heating pad will be applied over it (see details in Manual of Procedures) and set to induce a skin temperature of $42.0 \pm 2^{\circ}$ C for 1 hour then removed, and the patch will be kept on for another 7 hours (patch will be applied for a total of 19 hours), then it will be removed. Each subject will receive a naltrexone hydrochloride 50 mg oral tablet 12 ± 1 hour and shortly prior to patch application and then every 12 ± 1 hour for 8 additional doses, then one dose every 24 ± 2 hours for two more doses. A total of twelve 50 mg oral doses of naltrexone will be administered.

Procedure Day 2: An **Apotex** (fentanyl) patch will be applied without heat for 18 hours, then a theratherm® heating pad will be applied over it and set to induce a skin temperature of $42.0 \pm 2^{\circ}$ C for 1 hour, then the patch and the heating pad will both be removed (patch will be applied for a total of 19 hours). Each subject will receive a naltrexone hydrochloride 50 mg oral tablet 12 \pm 1 hour and shortly prior to patch application and then every 12 ± 1 hour for 8 additional doses, then one dose every 24 ± 2 hours for two more doses. A total of twelve 50 mg oral doses of naltrexone will be administered.

Procedure Day 3: A **Duragesic**[®] patch will be applied without heat for 11 hours, then a theratherm® heating pad will be applied over it and set to induce a skin temperature of $42.0 \pm 2^{\circ}$ C for 1 hour then removed, and the patch will be kept on for another 7 hours (patch will be applied for a total of 19 hours), then it will be removed. Each subject will receive a naltrexone hydrochloride 50 mg oral tablet 12 ± 1 hour and shortly prior to patch application and then every 12 ± 1 hour for 8 additional doses, then one dose every 24 ± 2 hours for two more doses. A total of twelve 50 mg oral doses of naltrexone will be administered.

Procedure Day 4: A **Duragesic**[®] patch will be applied without heat for 18 hours, then a theratherm® heating pad will be applied over it and set to induce a skin temperature of $42.0 \pm 2^{\circ}$ C for 1 hour, then the patch and the heating pad will both be removed (patch will be applied

for a total of 19 hours Each subject will receive a naltrexone hydrochloride 50 mg oral tablet 12 \pm 1 hour and shortly prior to patch application and then every 12 \pm 1 hour for 8 additional doses, then one dose every 24 \pm 2 hours for two more doses. A total of twelve 50 mg oral doses of naltrexone will be administered.

Procedure Day 5: A **Mylan** (fentanyl) patch will be applied without heat for 11 hours, then a theratherm® heating pad will be applied over it and set to induce a skin temperature of $42.0 \pm 2^{\circ}$ C for 1 hour then removed, and the patch will be kept on for another 7 hours (patch will be applied for a total of 19 hours), then it will be removed. Each subject will receive a naltrexone hydrochloride 50 mg oral tablet 12 ± 1 hour and shortly prior to patch application and then every 12 ± 1 hour for 8 additional doses, then one dose every 24 ± 2 hours for two more doses. A total of twelve 50 mg oral doses of naltrexone will be administered.

Procedure Day 6: A **Mylan** (fentanyl) patch will be applied without heat for 18 hours, then a theratherm® heating pad will be applied over it and set to induce a skin temperature of $42.0 \pm 2^{\circ}$ C for 1 hour, then the patch and the heating pad will both be removed (patch will be applied for a total of 19 hours). Each subject will receive a naltrexone hydrochloride 50 mg oral tablet 12 \pm 1 hour and shortly prior to patch application and then every 12 ± 1 hour for 8 additional doses, then one dose every 24 ± 2 hours for two more doses. A total of twelve 50 mg oral doses of naltrexone will be administered.

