7 PHARMACOKINETICS AND STATISTICAL CONSIDERATIONS

7.1 Study Hypotheses

Due to differences in inactive ingredients between reference and generic fentanyl transdermal patches the release rate of fentanyl may differ from these patches upon exposure to heat. As a result, in this study the influence of standardized heat application (two heat periods) on the pharmacokinetics (PK) parameters of fentanyl will be studied after using Duragesic[®] (reference), Apotex (fentanyl) (generic), and Mylan (fentanyl) (generic) transdermal patches.

The primary analysis will be to determine whether heat differentially impacts fentanyl serum concentrations among Duragesic[®] (reference), Apotex (fentanyl), and Mylan (fentanyl) transdermal patches. We will test the null hypothesis (H₀) that the coefficient for the patch-by-heat interaction equals zero, adjusting for time.

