7.2 Pharmacokinetics (PK) Analyses

Fentanyl concentrations will be measured in serum samples collected from each subject from the opposite arm to which the fentanyl system will be applied. Blood samples (approximately 5 mL) will be collected during each procedure day, 15 min before patch application and then at 1:00, 10:00, 10:55, 11:05, 11:15, 11:25, 11:35, 11:45, 12:00, 13:00, 14:00, 16:00, 17:00, 17:55, 18:05, 18:15, 18:25, 18:35, 18:45, 19:00 20:00, 21:00 and 22:00 hr post-patch application. The fentanyl PK parameters to be estimated using non-compartmental analysis (NCA) after each system application are: maximum serum concentration (Cmax) at different time intervals; 0-11, 0-19, 0-22, 11-12, 12-18, 18-19 and 19-22 hr; apparent elimination rate constant (k); apparent half-life (t1/2), calculated as 0.693/k; AUC of the serum concentration–time at different time intervals; 0-11, 0-19, 0-22, 11-12, 12-18, 18-19 and 19-22 hr determined by the linear trapezoidal method; and AUC value extrapolated to infinity (AUCinf), calculated as the sum of AUC₂₂ and the area extrapolated to infinity: AUCinf = AUC₂₂ + C₂₂/k where C₂₂ would be the last quantifiable concentration. All NCA analyses will be conducted using Phoenix® WinNonlin[®] 6.3 (Pharsight, a Certara Company, CA).

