7.3 Final Analysis Plan

The main objective of this study is to investigate the influence of heat application on the PK parameters of fentanyl after using reference and generic patch products. The primary PK parameters to be compared are 1) Cmax, before and after heat application and 2) AUC before and after heat application consistent with similar PK studies [4, 5, 7, 8, 16-22]. Analysis of variance (ANOVA) followed by post-hoc Bonferroni test will be used for comparing the differences in the means of the PK parameters and significant differences will be declared at p < 0.05. The statistical comparisons will be conducted as follow:

Three pair-wise comparisons between the patches (Apotex v Mylan; Apotex v Duragesic[®]; and Mylan v Duragesic[®]) will be performed using the results of a three-way repeated-measures ANOVA. The model will include time, type of patch (e.g., Apotex or Mylan), application of heat (yes or no), and interaction between patch and application of heat. The time term comprises multiple indicator variables for maximum model flexibility to perform the comparison at different time points specified above. We will test the null hypothesis that the coefficient for the patch-by-heat interaction equals zero, adjusting for time.

If fentanyl concentrations are found to be non-normally distributed, then we will examine Box-Cox transformations (e.g., log, square-root, etc.) that can achieve normality. If no transformation can achieve normality, then we will use permutation tests to compute empirical p-values, and we will use the bootstrap to compute standard errors and confidence intervals that account for within-person correlation.

A secondary analysis will assess the effects of heat and time on fentanyl within a patch. Specifically, the ANOVA will also include interaction terms of time with patch and heat, and a three-way interaction between time, heat, and patch. Inclusion of the three-way term allows the effects of heat on fentanyl to differ by patch. Testing the time-by-heat interaction, separately for each patch, using the same procedure outlined above produces estimates of intra-procedure effects.

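### The six conditions appear to run in one fixed order with no period term, so product levels and single-window heat contrasts cannot be separated from session

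*Combined protocol and SAP*

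**What the plan says.** The Protocol Summary and Section 4 of the combined protocol and SAP give each numbered procedure day one product and one heat time:

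| Procedure day | Product | Heat applied |
|---|---|---|
| 1, 2 | Apotex | 11-12 h, then 18-19 h |
| 3, 4 | Duragesic | 11-12 h, then 18-19 h |
| 5, 6 | Mylan | 11-12 h, then 18-19 h |

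The last entry in the Summary, for Day 6, is heat "18 hours after application of the Mylan (fentanyl) transdermal patch". Section 4 states "Each of the 10 subjects will be enrolled to complete all six procedure days (Procedure Days 1 to 6", with at least two weeks between days. After each day an independent safety monitor reviews the data "to determine whether or not to proceed to the next procedure day". The available text mentions no randomisation, sequence allocation or counterbalancing.

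Section 7.1 gives the primary aim as "to determine whether heat differentially impacts fentanyl serum concentrations among" the three patches, tested through the patch-by-heat interaction. Section 7.2 lists "maximum serum concentration (Cmax) at different time intervals; 0-11, 0-19, 0-22, 11-12, 12-18, 18-19 and 19-22 hr", and AUC over the same intervals. Section 7.3 says: "The model will include time, type of patch (e.g., Apotex or Mylan), application of heat (yes or no", plus the patch-by-heat interaction. Its time term refers to sampling times within a session. It also plans "Three pair-wise comparisons between the patches" and a comparison of PK parameter means. Neither the primary nor the secondary model contains a period, session or sequence term.

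**The concern.** If every subject takes the conditions in the numbered order, product and session are the same variable. Anything that changes over the study, such as assay performance, season, subject habituation or staff technique, then appears as a product difference. The within-subject design removes differences between subjects but not differences between sessions.

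Heat contrasts within a single window have the same problem. At 11-12 h, the heated arm for each product is its first session and the unheated arm its second; at 18-19 h this is reversed.

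The study is meant to inform policy on whether generic patches respond to heat as the reference does. A difference in level could be credited to formulation when it is due to order. So could a difference in heat effect, if the heat effect itself changed over the sessions.

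Fentanyl carryover is not the mechanism. At the stated 24 h half-life, 14 days is 14 half-lives, and 1 - 0.5^14 = 99.99% is eliminated.

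**Working it through.** The documents give no power calculation and no session-effect size, so there is no plan figure to reproduce. The design structure comes from Sections 4, 7.2 and 7.3. **All drift sizes below are assumptions.**

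**1. Can condition be separated from period?** A session-level model has 10 subject + 5 period + 5 condition = 20 columns.
- One order: rank 15, so none of the 5 condition contrasts is estimable once period is fitted.
- Williams sequences: rank 20.

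A full period term therefore cannot be added while the order stays fixed.

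**2. Product levels.** Mean session number is 1.5 (Apotex), 3.5 (Duragesic) and 5.5 (Mylan). A drift of b per session biases Mylan v Apotex by 4b and each other pair by 2b.

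| Drift per session | Mylan v Apotex | Each other pair |
|---|---|---|
| 1% | about 4% | about 2% |
| 2% | 1.02^4 - 1 = 8.2% | 1.02^2 - 1 = 4.0% |
| 5% | 20% additive; 1.05^4 - 1 = 21.6% | 10% additive; 1.05^2 - 1 = 10.3% |

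The shortest span from Day 1 to Day 6 is 5 x 14 = 70 days.

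**3. Heated versus unheated in one window.** The bias is -b at 11-12 h and +b at 18-19 h, so a 2% drift gives -2% and +2%. A linear drift cancels in the single-window patch-by-heat term, but an irregular one does not: a 10% effect on Day 5 alone moves the Mylan term by +10% at 11-12 h or -10% at 18-19 h.

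**4. Primary model, both windows.** There are 23 post-application sampling times, so 6 x 23 = 138 session-time cells. The columns are 23 time + 2 patch + 1 heat + 2 interaction = 28. Each heated hour contains 6 samples.
- *Heat coded only for heated samples:* additive day effects (linear 2%, or 10% on Day 5 only) give zero bias in patch-by-heat.
- *Heat coded from onset onward:* the linear drift gives zero interaction bias, but the 10% Day 5 effect leaves 0.0513, or 5.1%, in the Mylan term.
- *Session terms in place of patch:* 23 + 5 + 3 = 31 columns, rank 31. The 5.1% falls to zero.

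**5. Multiplicative drift on the raw scale.** Assume 2% per session, heat coded for heated samples only, and a profile rising linearly to a plateau at 12 h and decaying with a 24 h half-life after 19 h.

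| True heat effect | False Mylan-Apotex interaction, as share of the heat effect | As share of plateau |
|---|---|---|
| 10% | 14.1% | 1.4% |
| 20% | 11.2% | 2.2% |
| 50% | 9.4% | 4.6% |

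On the log scale it is zero. Session terms do not remove it on the raw scale.

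**6. A heat effect that drifts.** At 2 points per session, the interaction bias is 2 x 2 = 4 points (Duragesic v Apotex) and 2 x 4 = 8 points (Mylan v Apotex). Session number equals 2 x product index + late-heat indicator + a constant. A heat-by-session trend is therefore aliased once heat-by-product and heat-by-window are both fitted, and can be separated only by assuming that heat acts equally at 11 h and 18 h.

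**The case against.** **The fixed order is inferred.** No sentence says that all subjects share it, and the day numbers could be labels for conditions. The part of the protocol between the Summary and Section 2, and the Manual of Procedures, were not available. Staggered entry is possible: the study is to last "Approximately 18 weeks including the screening period" against about 12 weeks per subject, so calendar effects that are not linear would be only partly aliased with session. This limits confidence. But the numbering and the day-to-day safety review favour a chronological order, and if orders do differ, the allocation is still unstated in the available text and the period term still missing.

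**The primary test is not the main casualty.** This is right. The three pairwise patch comparisons may be meant as interaction contrasts, and the before-and-after comparisons as within-session ones, which are not aliased with session. Even so, Section 7.3 also compares PK parameter means, and Section 3.2 lists Cmax, Tmax and AUC with and without heating for each patch. Level and single-window contrasts are therefore not excluded.

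**Heat coding and scale are specification points that can be fixed without reordering.** Also right, and Section 7.3 allows a log transformation, but only if the data are non-normal. Most of the raw-scale interaction restates the 8.2% level drift.

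**A drifting heat effect is hypothetical.** The same target skin temperature applies on every day, and the documents give no evidence of drift. It is, however, the one gap that coding and scale cannot close. The primary model has no heat-by-window term, so it already assumes equal heat effects at 11 h and 18 h without saying so.

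**Conclusion.** The concern holds on the natural reading of the plan, with medium confidence because the common order is inferred. Between-product Cmax and AUC levels, and single-window heat contrasts, cannot be told apart from session. At an assumed 1% to 5% drift per session, the level bias is about 4% to 22% for Mylan v Apotex and 2% to 10% for each other pair.

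The primary interaction is affected less. Its bias from additive day effects is zero if both windows are used and only heated samples are coded as heated. The plan secures neither that coding nor the log scale, and a heat effect that drifts would still look like a product difference in heat sensitivity. This should be fixed, but it does not by itself invalidate the primary test.

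**What to change.** **Preferred.** Randomise each subject to one of the six sequences of a Williams square over the six product-by-heat-time conditions, and add period to the model. With 10 subjects, four sequences are used twice and two once. Efficiency for a product contrast is then 97.0% to 99.5% (mean 98.4%) over all labellings of the square; 12 subjects would balance exactly. Period uses 5 of the 59 - 9 - 5 = 45 within-subject error degrees of freedom in a session-level analysis, leaving 40.

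This needs a protocol amendment, a randomisation list and all three products on hand from the first session. Visits, patches and samples are unchanged. The safety review would stay after each round but would cover mixed conditions, which the sponsor and the safety monitor would have to accept.

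**If the order cannot change.** Amend the analysis text only:
- analyse on the log scale and use both windows;
- define heat sample by sample, as yes only for samples taken during heating;
- replace the patch main effect by session terms, so that heat contrasts are within session (with complete data and the coding above this leaves the heat point estimates unchanged, but it protects against other codings);
- tabulate the heat effect by session as description only, since under one order the table cannot separate drift from product;
- report between-product Cmax and AUC level differences as confounded with order, and state the assumption of equal heat effects at 11 h and 18 h.

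**If subjects already take different orders.** State how sequences are allocated and add the period term.
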